## **9.2. Exposure and Compliance**

The duration of study drug exposure is defined as the number of days on treatment from the first dose of study drug until the last dose of study drug (last dose – first dose + 1). Study drug exposure is summarized by descriptive statistics. Summaries include the total dose (mg) received (based on the number of pills returned), study drug compliance, and duration (days) of exposure during the study treatment period. In addition, a summary of the number and percentage of patients exposed by dose (placebo, 5 mg, 10 mg, 20 mg, 30 mg) and by visit is generated. If a patient received more than one dose during a visit window, the duration of the longest dose is used to calculate exposure. Summaries of the number and percentage of patients exposed by dose include subgroup analyses by baseline UACR (UACR  $\leq$  300 mg/g vs. UACR  $>$  300 mg/g).

Total number of doses dispensed and total dose (mg) dispensed is calculated from total number of kits (bottles) recorded on the Study Drug Dispensation eCRF. Total number of doses received is calculated from information on the eCRF of Study Drug Return and Study Drug Dispensation, as the (total number of doses dispensed – total number of doses returned). If a kit is not returned but the patient had a subsequent dispensation, then the non-returned kit is assumed to have been taken in full. However, if a kit is not returned and no kit is subsequently dispensed, then the non-returned kit is assumed to not have been taken. Study drug compliance (%) is calculated as  $100 \times$  total number of doses received / total number of study days of study participation, excluding the off-treatment period.

Patients not at per-protocol dose are listed including reasons.

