### 10.2. Study Drug Packaging and Labeling

The study drug will be supplied as either individual bottles (5 mg dose) or in tamper-evident kits containing two high-density polyethylene bottles (10 mg, 20 mg, and 30 mg doses) or the matching placebo capsules. Each bottle will utilize foil induction-seal liners and a child-resistant closure. Each bottle of study drug will contain 30 capsules of bardoxolone methyl or matching placebo. Each bottle will also contain a desiccant insert that must not be ingested. Labeling on each kit bottle will contain at minimum the following information:

- Medication ID number;
- Bardoxolone methyl capsules (strength) or matching placebo
- Protocol 402-C-2002;
- Caution Statement: New Drug – Limited by Federal Law to Investigational Use.
- Keep out of reach of children;
- Control or lot number;
- Store at 15° – 25°C (59° – 77°F);
- Reata Pharmaceuticals, Inc., [name].

When applicable, a double-panel label will be presented on the treatment kit carton containing this and other information as well. Additionally, labeling, in the relevant local languages for investigational medicinal product for use and distribution in the European Union shall adhere to current Eudralex, Volume 4 Annex 13 guidance and requirements.

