### **10.7. Compliance**

The prescribed dosage, timing, and mode of administration of study drug may not be changed. Patients will be asked questions regarding compliance and any departures from the intended regimen must be recorded in the eCRF. Patients will be asked to return all unused study drug. Non-compliance is defined as taking less than 80% or more than 120% of study drug during any evaluation period (visit to visit).

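### SAP 9.2 counts an unreturned kit as 30 doses taken, or as none if it is the last kit, which misstates compliance and total dose for the patients affected

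*SAP*

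**What the plan says.** SAP Section 9.2 obtains doses received by subtracting what is returned from what is dispensed, so it needs a rule for kits that never come back. For any kit that was followed by a later dispensing: "the non-returned kit is assumed to have been taken in full". For the last: "if a kit is not returned and no kit is subsequently dispensed, then the non-returned kit is assumed to not have been taken". Compliance is 100 times "total number of doses received / total number of study days of study participation, excluding the off-treatment period". Total mg received also rests on the count of returned pills. No upper limit is placed on any of these. Duration of exposure, in the same section, is instead taken from the first and last dose dates.

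On supply, Protocol Section 10.2 states: "Each bottle of study drug will contain 30 capsules of bardoxolone methyl or matching placebo". The 5 mg dose is one bottle. The 10, 20 and 30 mg doses are two-bottle kits made from 5 mg and 15 mg capsules (Protocol Section 10.1). Each bottle or kit therefore holds 30 daily doses.

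Protocol Section 9.10.14 dispenses at Day 1 and Weeks 2, 4, 6 and 8, with Week 6 only when the baseline albumin-to-creatinine ratio is above 300 mg/g. Protocol Section 7.6.3 lists Week 6 dispensing without that condition. Used kits are due back at the following visit. Dosing is once daily, doubling up is forbidden, and the last dose falls on the day before the Week 12 visit (Protocol Section 9.10.13).

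**The concern.** A kit holding 30 doses but meant to cover 14 days should come back with about 16 doses left. If it is lost, the rule treats those 16 as swallowed, which once-daily dosing without doubling does not allow. The last kit, dispensed at Week 8, covers 28 of the 83 dosing days. If it is lost, all 28 days are scored as missed, even where the recorded last-dose date shows that the patient was still dosing on Day 83.

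At stake is whether the compliance and total-dose tables can be read at face value. The two errors run in opposite directions, so a group mean that looks reasonable does not show that either is absent. SAP Section 9.2 could also report, for the same patient, 83 days of exposure and no doses in the last 28 of them.

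**Working it through.** The documents give no compliance or total-dose figure to reproduce. The check applies SAP Section 9.2 to a patient who takes every dose.

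**Inputs**
- 30 daily doses per bottle or kit (Protocol Sections 10.1, 10.2).
- Visits on Days 1, 14, 28, 42, 56 and 84; last dose on Day 83.
- Doses of 5, 10 and 20 mg from Day 1, Week 2 and Week 4, then 30 mg from Week 6 only if baseline UACR exceeds 300 mg/g (Protocol Section 7.4.1). The mg figures are for a fully titrated patient on active drug.
- Denominator of 84 days (assumed; the SAP does not say whether the visit day counts).

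**True doses**
- UACR > 300: 13 + 14 + 14 + 14 + 28 = 83. Total = 65 + 140 + 280 + 420 + 840 = 1745 mg.
- UACR ≤ 300, no Week 6 kit: 13 + 14 + 28 + 28 = 83. Total = 65 + 140 + 560 + 560 = 1325 mg.
- True compliance = 83/84 = 98.8%.

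**Formula.** Doses credited = 83 − (doses actually taken from the lost kit) + 30 for a non-final kit, or + 0 for the final kit. Compliance = 100 × doses credited / 84.

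| Lost | Doses credited | Compliance | Total mg (against true) |
|---|---|---|---|
| **UACR > 300** | | | |
| Day 1 bottle | 83 − 13 + 30 = 100 | 119.0% | 1830 (+4.9%) |
| Week 2 kit | 83 − 14 + 30 = 99 | 117.9% | 1905 (+9.2%) |
| Week 4 kit | 99 | 117.9% | 2065 (+18.3%) |
| Week 6 kit | 99 | 117.9% | 2225 (+27.5%) |
| Two of the Week 2, 4, 6 kits | 115 | 136.9% | 2225 to 2545 (+27.5% to +45.8%) |
| Week 8 kit (final) | 83 − 28 + 0 = 55 | 65.5% | 905 (−48.1%) |
| **UACR ≤ 300, no Week 6 kit** | | | |
| Day 1 bottle | 100 | 119.0% | 1410 (+6.4%) |
| Week 2 kit | 99 | 117.9% | 1485 (+12.1%) |
| Week 4 kit | 83 − 28 + 30 = 85 | 101.2% | 1365 (+3.0%) |
| Day 1 bottle and Week 2 kit | 116 | 138.1% | 1570 (+18.5%) |
| Week 8 kit (final) | 55 | 65.5% | 765 (−42.3%) |

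**Variants**
- With an 83-day denominator, one lost 14-day kit or Day 1 bottle gives 119.3% to 120.5%, and a lost final kit gives 66.3%.
- With the Week 12 visit on Day 81, a lost final kit gives 55/81 = 67.9%.
- With the Day 1 bottle and the Week 8 kit both lost, the errors partly cancel: (83 + 17 − 28)/84 = 72/84 = 85.7%.
- A patient lost after Day 1 with the only bottle unreturned is credited with 0 doses, although the first dose is given in clinic (Protocol Section 7.6.2).

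**The case against.** The best defence is that little depends on these numbers, and most of it stands.

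A reader might infer that the exposure basis for the safety objective is distorted. The documents do not support that. Exposure duration uses dose dates. The safety population needs a single dose (SAP Section 5.3.2). Adverse event percentages use patients per treatment group (SAP Section 5.2), treatment-emergent status uses dose dates (SAP Section 9.1), and no formal safety testing is planned (SAP Section 9). No per-protocol set is defined, so compliance selects no one into or out of an analysis.

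A reader might also divide 30 by 14 and report 214% compliance for an interval, or say that anyone who loses a kit falls on the wrong side of the Protocol Section 10.7 rule: "Non-compliance is defined as taking less than 80% or more than 120% of study drug during any evaluation period". SAP Section 9.2 plans neither interval-level compliance nor a summary by those limits. On the planned whole-treatment figure over 84 days, one lost non-final kit stays below 120%.

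The size also depends on Week 6 dispensing. Under Protocol Section 9.10.14, patients with UACR of 300 mg/g or less have about two 14-day and two 28-day intervals, so it is not true for them that most intervals are 14 days.

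Zero for the final kit can be defended as a lower bound, and it is close to right for someone who stopped soon after Week 8. That defence fails where the last-dose date shows later dosing. Finally, kits must be returned and capsules counted (Protocol Sections 9.10.14, 10.5), and SAP Section 5 provides listings with source data, so affected patients could be traced. Listings do not correct the summary tables.

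**Conclusion.** The concern holds as a minor point about descriptive summaries. Followed as written, SAP Section 9.2 misstates doses received, total mg and overall compliance for patients with an unreturned kit. For a fully adherent patient the true 98.8% becomes about 118% with one lost 14-day kit, about 137% with two, and about 66% with the final kit lost. In the last case total dose is 42% (UACR ≤ 300) to 48% (UACR > 300) too low. For a patient with UACR ≤ 300 and no Week 6 kit, a lost Week 4 kit adds only 2 doses.

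These figures assume perfect adherence, visits on target days and an 84-day denominator; the variants move them by about two percentage points. The documents give no expected number of unreturned kits, so the effect on group means cannot be stated. Exposure duration, adverse event percentages, analysis sets and the eGFR analyses are unaffected.

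**What to change.** Replace both rules in SAP Section 9.2 with one that covers every unreturned kit, including the final one. Doses taken should be no more than the days from its dispensing to the next dispensing or to the last-dose date, whichever is earlier, never more than the 30 doses in the kit, less missed doses or interruptions recorded in the eCRF. State the day count: next dispensing date minus dispensing date, or last-dose date minus dispensing date plus 1. For the patient above this gives 13 + 14 + 14 + 14 + 28 = 83 doses and 98.8%, whichever kit is lost.

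Calculate total mg from the capped doses and report by arm the number of patients with an imputed kit. State the denominator day count. Reconcile Protocol Sections 7.6.3 and 9.10.14 on Week 6 dispensing, because the interval for the Week 4 kit depends on it.

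The cost is a little programming with dates SAP Section 9.2 already uses or that accompany dispensing records. Protocol Sections 8.3.1 and 10.7 send temporary discontinuations and departures from the regimen to the eCRF. The diary holds every administered and missed dose (Protocol Section 9.4), but the documents do not say that its dosing entries reach the eCRF, so the rule should not depend on them. The drawback is that full adherence is assumed between known dates wherever no missed dose is recorded.

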## **9.3. Concomitant Medications**

Concomitant medications are coded using the World Health Organization (WHO) drug dictionary (Enhanced version, March 2019, B3 format) for anatomical therapeutic chemical classification (ATC) and preferred drug name. A patient who used multiple medications is counted only once for each ATC and preferred drug name. ATC and preferred drug name within each ATC are sorted alphabetically. Coded concomitant medications are summarized by treatment by WHO ATC class and preferred name. A patient who used multiple medications is counted only once for each ATC and preferred drug name. Percentages are based on the number of patients in the safety analysis set. Each summary is ordered by descending order of incidence of ATC class and preferred name within each ATC class. Concomitant medications will be summarized by treatment year and overall.

A concomitant medication is any medication taken at the time of first study treatment or a medication that was started after the start of study drug dosing. Specifically, concomitant medications are medications

- that are continued from screening and continued after the first study drug dosing, or
- that have start dates or stop dates within the treatment period, or
- that have no end date.

Medications with an end date on the date of first study drug administration are not considered concomitant medications.

Patients who take excluded medications (defined in the Protocol Section 9.3.1) during the study are listed.

### **9.3.1. Missing and Partial Concomitant and Other Medication Start and Stop Dates**

Missing and partial concomitant medication start and stop dates are detailed in Section [5.6.1.3](#).

## **9.4. Prior and Concomitant Procedures and Surgeries**

Prior and concomitant procedures and surgeries are listed.

## **9.5. Clinical Laboratory Evaluations**

Laboratory data are summarized at baseline and at each time point by treatment.

### **9.5.1. Continuous Summaries of Laboratory Results**

Laboratory evaluations and change from baseline are summarized by treatment, laboratory category (hematology, chemistry, urinalysis and microscopy), test, and study visit using continuous statistics. The estimated glomerular filtration rate (eGFR) results are calculated using formulas described in Section [5.5.5](#).

The change from baseline in select laboratory evaluations at the protocol-defined on treatment endpoint time points (i.e., Week 1,2,4,6,8, and 12) for patients treated with bardoxolone methyl compared to placebo may be performed using MMRM model described in Section [7.4](#) and the ANCOVA sensitivity analysis described in Section [7.4.1.1](#).

The change from baseline in select laboratory evaluations at the protocol-defined off treatment endpoint time points (i.e., Day 0,3,7,14,21,28, and 35) for patients treated with bardoxolone methyl compared to placebo may be performed using MMRM model described in Section [8.1](#).

Box plots and line graphs are generated for selected laboratory test results, such as eGFR, UACR, alanine aminotransferase (ALT), aspartate aminotransferase (AST), total bilirubin, BNP, BUN, uric acid, magnesium, creatinine, and creatine kinase (CK). Line graphs include mean  $\pm$  SE over time for both the observed values and for change from baseline.

Summaries of continuous statistics are provided for the following urinalysis parameters: albumin, creatinine, pH, erythrocytes, and specific gravity. Qualitative lab results are included in the listings but are not summarized. Laboratory results that are above or below normal limits are flagged in the listings.

Summaries of UACR (Section 5.5.6) will use the geometric mean (with standard error) with 95% confidence intervals instead of the arithmetic mean and will display UACR results in original units of mg/g. Changes from baseline in UACR are calculated as the ratio of each visit to baseline and reported as the post-baseline/baseline ratios and are summarized by geometric means with 95% confidence intervals at each time point. Similar On Treatment MMRM analyses as described in Section 7.4.1 and the ANCOVA analysis described in Section 7.4.1.1, will be performed for UACR ratio to baseline. The change from baseline for UACR ratio to baseline at the protocol-defined endpoint time points Week 17 for patients treated with bardoxolone methyl compared to placebo may be performed using the ANCOVA models described in Section 7.4.1.1 and Section 8.1.1.1. Additionally, UACR is summarized by baseline UACR quartile. Summaries of UACR include values for scheduled visits.

#### 9.5.1.1. Natural log(UACR)/eGFR

Mean ratios of natural log(UACR)/eGFR (Section 5.5.8) are summarized at each time point. The ratio of natural log(UACR)/eGFR by analysis visit is summarized by arithmetic means.

#### 9.5.2. Categorical Summaries of Laboratory Results

Select laboratory parameters will be summarized using shift tables. Shift tables are summarized by treatment, laboratory category (hematology, chemistry, urinalysis, and microscopy), and laboratory test and present shifts from baseline status (Normal, Low, High) to worst on study treatment status (Normal, Low, High). The worst abnormality values are defined as the maximum values while on study treatment, with the exception of magnesium and hemoglobin. The worst abnormal values for magnesium and hemoglobin are defined as the minimum values while on study treatment.

Additionally, laboratory parameters of specific interest (ALT, AST, UACR) are summarized using shift tables that summarize shifts from (1) baseline status to end of treatment status, (2) worst on-treatment status to worst off-treatment status (3) worst on-treatment status to Day 35 off-treatment status, and (4) baseline status to worst on-treatment status (5) baseline to worst off-treatment, and (6) worst on-treatment status to best (lowest) off-treatment status. The number and percentage of patients are summarized. For UACR, summaries will present shifts from/to the categories listed in Section 5.5.6.1. For ALT and AST, summaries will present shifts from/to the following categories:

- $\leq$  ULN
- $>$  ULN to  $\leq$  3x ULN
- $>$  3x ULN

In addition, a summary table is provided for the number and percentage of patients meeting the following threshold levels at any time during the study:

- $>$  5x ULN for more than 2 weeks
- $>$  3x ULN and (TBL  $>$  2x ULN or INR  $>$  1.5)
- $>$  3x ULN with the appearance of fatigue, nausea, vomiting, right upper quadrant pain or tenderness, fever, rash, and/or eosinophilia ( $>$  5%).

- BNP > 200 pg/mL
- Magnesium < 1.3 mEq/L (0.65 mmol/L)
- NT-proBNP > 1000 pg/mL

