### **9.1.3. Management of Muscle Spasms**

Basic symptomatic relief is the first step in managing muscle spasm, including walking, adequate hydration, wearing socks, and stretching before bedtime. Assessment of levels of electrolytes such as magnesium, calcium, and potassium may indicate the need for replacement. Serum vitamin D levels may be collected by the investigator, in the evaluation of muscle spasms. If vitamin D levels are low, supplementation may be warranted. Muscle relaxants may also help relieve symptoms.

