### **9.1.7. Management of Blood Pressure**

Investigators should attempt to maintain the blood pressure within the range recommended by the Kidney Disease Blood Pressure Working Group :  $\leq 140$  mmHg systolic and  $\leq 90$  mmHg diastolic for patients with UACR  $< 30$  mg/g, and  $\leq 130$  mmHg systolic and  $\leq 80$  mmHg diastolic for patients with UACR  $> 30$  mg/g ([KDIGO, 2012](#)).

Patients being treated with an ACEi and/or ARB should be receiving the maximally tolerated labeled daily dose (MTLDD), defined as the dose at or below the labeled dose that does not exhibit any intolerable adverse effects (e.g., hypotension, hyperkalemia), based on the investigator's assessment. If the patient is currently receiving one drug (ACEi or ARB) below the maximum labeled dose, the drug should be titrated to the MTLDD based on the assessment of tolerability by the investigator at least 6 weeks prior to the Screen A visit.

Diuretics may be titrated to help maintain blood pressure target levels.

Any changes in ACEi or ARB use or diuretic therapy should be preceded by consideration of any relevant contraindications as per the local product information.

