#### **9.10.18. Clinical Chemistry**

Samples will be collected for the following clinical chemistry analyses as indicated in [Table 4](#): ferritin, CK, BUN, enzymatic creatinine, eGFR, TBL, direct bilirubin, ALT, AST, ALP, sodium, potassium, calcium, phosphorus, uric acid, total protein, glucose, albumin, LDH, magnesium, chloride, bicarbonate, and GGT.

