#### **9.10.22. Hematology**

Samples will be collected for the following hematology assessments as indicated in [Table 4](#): hematocrit, hemoglobin, red blood cell (RBC) count, white blood cell (WBC) count, neutrophils, bands (if detected), lymphocytes, monocytes, basophils (if detected), eosinophils (if detected), absolute platelet count, mean corpuscular hemoglobin (MCH), mean corpuscular volume (MCV), and mean corpuscular hemoglobin concentration (MCHC).

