### 7.2. Statement of the Null and Alternate Hypothesis

The primary efficacy analysis compares the change from baseline in eGFR for patients randomized to bardoxolone methyl ( $\mu$  BARD) to the change from baseline in eGFR for patients randomized to placebo ( $\mu$  placebo) at the endpoint-specified visit according to the following hypotheses:

- Null hypothesis,  $H_0: (\mu \text{ BARD}) - (\mu \text{ placebo}) = 0 \text{ mL/min/1.73 m}^2$
- Alternative hypothesis,  $H_1: (\mu \text{ BARD}) - (\mu \text{ placebo}) \neq 0 \text{ mL/min/1.73 m}^2$

Because eGFR decreases with disease progression, an increase in eGFR relative to placebo is considered evidence of benefit.

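### SAP 9.5.2 takes the highest on-treatment value as the worst for every shift-table test but two, so any other test shows a patient as Low only if every value is low

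*SAP*

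**What the plan says.** SAP 9.5.2 opens with "Select laboratory parameters will be summarized using shift tables". It does not list the tests, but gives the categories as hematology, chemistry, urinalysis and microscopy. The tables "present shifts from baseline status (Normal, Low, High) to worst on study treatment status (Normal, Low, High"). The worst value is then defined by one general rule: "The worst abnormality values are defined as the maximum values while on study treatment, with the exception of magnesium and hemoglobin". For magnesium and hemoglobin it is the on-treatment minimum. No other exception is given, and there is no rule for a test that can be abnormal in both directions.

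Separate tables for ALT, AST and UACR have their own upward categories and are not in question. The threshold table in the same section has one low-side item, magnesium, which already has the minimum rule.

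The protocol collects many tests that can be abnormally low. Hematology (Protocol 9.10.22) starts with "hematocrit, hemoglobin, red blood cell (RBC) count, white blood cell (WBC) count, neutrophils" and goes on to lymphocytes and platelets, among others. Clinical chemistry (Protocol 9.10.18) includes sodium, potassium, calcium and phosphorus, and ends with "total protein, glucose, albumin, LDH, magnesium, chloride, bicarbonate, and GGT".

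**The concern.** A shift table is read as showing how many patients in each arm moved out of range at their worst point. Under a maximum rule, the Low cell for a test where low values matter instead counts patients who were low at every draw. Patients with intermittent low values go into Normal, so the table understates the number with a low on-treatment value.

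Safety and tolerability is one of the two primary objectives. The trial has about 70 patients and no formal safety testing (SAP 9), so descriptive patient counts by arm carry much of the laboratory safety picture.

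**Working it through.** The plan states no figure on this point, so there is none to reproduce. The check is of the rule itself.

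**Inputs**
- Worst-value rule and three-level status: SAP 9.5.2.
- Scheduled on-treatment draws: Weeks 1, 2, 4, 6, 8 and 12, so six (Protocol 7.6.3 and 7.6.4). The Week 12 draw follows the last dose by one day, and SAP Table 4 counts assessments less than 2 days after the last dose as on treatment.
- Panels: 23 chemistry tests (Protocol 9.10.18) and 14 hematology tests (Protocol 9.10.22).

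**1. What Low requires.** For values x1 to xk and lower limit LLN, max(x1, ..., xk) < LLN if and only if every xi < LLN. Examples in arbitrary units, normal range −1 to 1:

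| Six on-treatment values | Maximum rule | Minimum rule |
|---|---|---|
| −2, −2, −2, −2, −2, −0.5 | Normal | Low |
| −2, 0, 2, 0, 0, 0 | High | Low |
| −2 at all six | Low | Low |

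The second row also shows that for a two-sided test one extreme cannot describe the patient.

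**2. Count of patterns.** With each draw either low or in range there are 2^6 = 64 patterns, and 64 − 1 = 63 contain a low value. One of these (six of six low) is shown as Low. The other 63 − 1 = 62 are shown as Normal. This counts patterns; it is not a probability.

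**3. Coverage of the minimum rule.** Chemistry 1 of 23 (magnesium), hematology 1 of 14 (hemoglobin), together 2 of 37. Many of the other 35 are upward-direction tests, such as ALT, AST, GGT and creatinine, for which the maximum is right.

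**4. Fit of the default to the documents' own use of the tests**
- Hemoglobin takes the minimum. Hematocrit and RBC count, from the same panel, would take the maximum.
- Inclusion criterion 6 sets lower limits for neutrophils and platelets beside hemoglobin, and exclusion criterion 9 sets one for albumin. Only hemoglobin has the minimum rule.
- Potassium is treated as two-sided. Protocol 9.1.3 says "Assessment of levels of electrolytes such as magnesium, calcium, and potassium may indicate the need for replacement", while Protocol 9.1.7 defines the tolerated background dose as one that "does not exhibit any intolerable adverse effects (e.g., hypotension, hyperkalemia").
- eGFR is in the chemistry panel, and SAP 7.2 says "Because eGFR decreases with disease progression, an increase in eGFR relative to placebo is considered evidence of benefit". Under the default its worst value would be its highest.

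**5. Repeat tests.** Protocol 9.7 allows unscheduled visits to repeat abnormal laboratory tests, and SAP 5.5.3 leaves open using unscheduled results for the worst post-baseline value. If they are used, one in-range repeat removes a patient from Low under the maximum rule.

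**6. Illustration with assumed rates.** The documents give no rate of low values. Assume a chance p of a low value at each of six draws, no high values, and a normal model with within-patient correlation ρ (simulated, except ρ = 0, where any low = 1 − (1 − p)^6 and all low = p^6):

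| p | ρ | Any low value | Shown Low under the maximum rule |
|---|---|---|---|
| 0.1 | 0 | 46.9% | 0.0001% |
| 0.1 | 0.5 | 31.9% | 0.4% |
| 0.1 | 0.9 | 18.2% | 4.1% |
| 0.3 | 0 | 88.2% | 0.07% |
| 0.3 | 0.5 | 66.8% | 4.4% |
| 0.3 | 0.9 | 45.1% | 17.1% |

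Even at ρ = 0.9, the share of patients with any low value who are shown as Low is 4.1/18.2 = 23% for p = 0.1 and 17.1/45.1 = 38% for p = 0.3.

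**7. What the other outputs give.** By-visit summaries include a minimum (SAP 5.2 and 9.5.1), which is one extreme per visit and not a patient count. Listings flag low values (SAP 9.5.1) but do not count them by arm. Adverse event tables count patients by arm (SAP 9.1.2), but only for changes judged clinically significant (Protocol 11.6).

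**The case against.** The strongest reply is that the point rests on a condition. The selected tests are unnamed, and marking two of them for the minimum fits an author who reviewed a chosen list. The default also matches the risks in Protocol 5.1.2: fluid overload with BNP, rises in ALT, AST and GGT, and rises in urinary albumin. Its one low-side laboratory risk is hypomagnesemia, and magnesium takes the minimum. The selected tests that SAP 9.5.1 names for plots number eleven, and of these only eGFR has an arguably wrong direction. Serum creatinine mirrors eGFR, so its maximum in effect captures the lowest eGFR. Protocol 5.1.2.3 lists raised potassium as the muscle-toxicity marker. With about 70 patients, low values could be counted from the flagged listings, and box plots and optional model-based comparisons of arms are also planned.

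Much of this stands as a limit on impact. The effect may be nil, and eGFR is the weakest example: it is analysed as the efficacy endpoint, and creatinine covers its low side. The pattern count says nothing about frequency. The 2 of 37 is a share of tests collected, not of tests tabulated, and leaves out urinalysis and microscopy.

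It does not remove the defect. The rule is written for every selected test, hematology is a named category, and Low is a reported status. A reader cannot tell from the SAP that the rule is harmless. The plot list is given by way of example and is for figures. The optional models compare mean changes, and a hand count from listings is not a planned output.

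**Conclusion.** The concern holds as a conditional one. SAP 9.5.2 states a rule that misclassifies patients for any selected test, other than magnesium and hemoglobin, in which low values matter; the SAP neither names the tests nor corrects the direction elsewhere. The logic needs no assumption about rates. The size in this trial is unknown: nil if only upward-direction tests plus the two exceptions are tabulated, and otherwise an understatement, for each affected test, of the patients with a low on-treatment value in each arm.

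It should be corrected, but it is not critical. The tables are descriptive, and no test, power figure or efficacy result depends on them.

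**What to change.** In SAP 9.5.2, replace the default-maximum rule with a named list of the shift-table tests and a direction for each:
- the on-treatment minimum where low values are the concern;
- the on-treatment maximum where high values are the concern;
- two separate shifts, baseline to minimum and baseline to maximum, where both are.

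The cost is a change of SAP wording, a direction flag per selected test in the programming, and a few more descriptive tables. Data collection does not change.
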